E-cigarettes present a potential innovative solution to the challenges of reducing tobacco smoking among adults with SMI. E-cigarettes provide an experience close to tobacco smoking, which may increase their acceptability and use. The long-term health consequences of e-cigarette use are unknown. However, no negative health consequences of short-term use as in the current study have been reported, and most researchers agree that e-cigarettes are likely healthier than tobacco smoking¹⁷. Importantly, two small open-label studies observed decreased tobacco smoking among non-treatment seeking adults with schizophrenia and schizoaffective disorder following one month of access to e-cigarettes^{18,19}. Such results are promising as individuals with schizophrenia exhibit severe tobacco smoking, even when compared to others populations with SMI.

In the current pilot proposal, adults with SMI (N=10/group) interested in reducing their tobacco smoking will be randomized to receive either nicotine replacement therapy (NRT; patch 21 mg) as the standard of care or NRT plus e-cigarettes (36 mg/ml) for one month according to a double-blind, randomized controlled trial design. We will use a previously evaluated e-cigarette including nicotine liquid solutions that have been independently tested.

SPECIFIC AIMS AND HYPOTHESES

Specific Aim 1: Assess feasibility, acceptability, and safety of providing e-cigarettes to adults with SMI to reduce tobacco smoking.

Hypothesis 1.a: *We predict that a high proportion of participants will consent to participate ($\geq 80\%$) and complete ($\geq 70\%$) the study.*

Hypothesis 1.b: *We predict that end of study participant satisfaction ratings will indicate high acceptability of e-cigarettes and likelihood of future use.*

Hypothesis 1.c: *We predict e-cigarettes will be safe as measured by frequency of adverse events (AEs) and side-effects. In addition, we predict e-cigarettes will not be associated with increases in symptom specific measures.*

Specific Aim 2: **To compare reductions in tobacco smoking between NRT vs NRT + e-cigarettes (36 mg/ml).**

Hypothesis 2: *Significantly greater reductions in smoking (tobacco cigarettes/day, breath CO) will be observed in the NRT + e-cigarette vs. the NRT condition.*

BACKGROUND AND RATIONALE

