Study Design and Overview. We will utilize a double-blind, randomized controlled design to assess the feasibility and acceptability of using e-cigarettes to reduce tobacco smoking among individuals with SMI (schizophrenia and schizoaffective disorder, bipolar disorder, or PTSD). Participants will consist of tobacco smokers with SMI interested in reducing or quitting their tobacco smoking. Note that these two experimental conditions were chosen based on available funds and likelihood of obtaining preliminary data that would be useful in a future NIH grant application. We plan to assess other conditions in the future (e.g., placebo e-cigarette, etc.). Following a one-week baseline lead-in period, participants will be randomized to either the NRT or NRT + e-cigarette condition. Study visits will be scheduled for once a week (5 weeks total).

[figure not shown]

Figure 1. Overview of study design.

Study Procedures and Assessments

Participant Recruitment and Selection. Participants will be recruited from the ICNTP, PIRL-M, and STARS clinic. Eligible participants will meet the following inclusion criteria: 1) be diagnosed with schizophrenia or schizoaffective disorder, bipolar disorder, or PTSD and in stable medical condition (DSM-5); 2) report smoking ≥ 10 tobacco cigarettes/day and present a breath CO ≥ 10 ppm; 3) report wanting to quit or reduce their cigarette smoking; 4) be fluent in English; 5) be between 18 and 65 years of age; and 6) have a stable living situation. Participants will be ineligible if they meet the following exclusion criteria: 1) be currently pregnant or breastfeeding; 2) report wanting to quit smoking in the immediate future; 3) test positive for illicit drugs except THC; and 4) have any illness, medical condition, or use of medications, which in the opinion of the study physicians (Drs. [name] and [name]) would preclude safe and/or successful completion of the study.

Following informed consent, participants will complete an initial general evaluation protocol (HSC-MS-05-0322; General evaluation of Eligibility for Substance Abuse/Dependence Research) to assess their psychiatric status, medical evaluation, and drug use history.

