E-cigarette. The e-cigarette will consist of 1) a 3.3 V, 1000 mAh battery; and 2) a 1.5 Ohm, dual-coil cartomizer (SmokTech; Shenzhen, China). Study staff will load the cartomizer with 1 ml tobacco flavored 70% propylene glycol/30% vegetable glycerin liquid containing nicotine concentrations 36 mg/ml (AVAIL; Richmond, Virginia, USA). Nicotine concentration will be tested at an independent laboratory at VCU (± 2 mg/ml). Virtually every aspect of the e-cigarette (model, voltage, resistance, liquid, and nicotine concentration) has been chosen based on systematically conducted studies by [name] and his colleagues³⁸⁻⁴¹. With these parameters, e-cigarettes with 36 mg/ml nicotine liquid produce blood plasma nicotine levels similar to that of tobacco cigarettes after 10 puffs. Participants will be provided verbal and written instructions on how to use and maintain the e-cigarettes at Week 1 visit. Risking of spilling nicotine liquid is minimal as the cartomizer contains cotton batting for liquid absorption. However, to mitigate any potential risks, participants will be provided gloves to be used when changing cartomizers. Additionally, they will receive pill bottles to hold spare cartomizers, instructed not to try and open the cartomizer, and told to keep them away from children.

Nicotine Replacement Therapy. Participants will receive nicotine patch (21 mg) starting study Week 1. Participants will be instructed to apply a new patch each morning on a clean, dry, non-hairy area of skin.

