E-Cigarette and Tobacco Smoking Related Assessments. Tobacco smoking will be assessed using a combination of breath CO, urinary cotinine, and self-report via time-line follow-back. Standard questionnaires will be used to assess a number of tobacco-smoking related measures. The Fagerstrom Test for Nicotine Dependence (FTND) will be used to assess tobacco cigarette dependence⁴². The Questionnaire of Smoking Urges (QSU) will be used to assess craving for tobacco cigarettes⁴³. The Minnesota Nicotine Withdrawal Questionnaire (MNWQ) will be used to assess withdrawal symptoms from tobacco cigarettes⁴⁴. The Stages of Change Questionnaire will be administered to assess desire to quit from tobacco cigarette smoking⁴⁵. The Clinical COPD Questionnaire (CCQ) will be used to assess changes in COPD-related symptoms⁴⁶. Additional smoking-related assessment will include the Confidence to Quit (CQ) and Hooked on Nicotine Checklist (HONC). E-cigarette related questionnaires developed and provided by [name] will be used to evaluate e-cigarette dependence, patterns of use, evaluation of using e-cigarettes, and side-effects. These questionnaires will include Confidence to Quit, E-Cigarette Dependence Scale, E-Cigarette Patterns of Use, E-Cig Evaluation, E-Cig Side Effects, and Hooked on Nicotine Checklist.

Assessing Changes in Symptoms Relevant to SMISchizophrenia. The Brief Psychiatric Rating Scale (BPRS)⁴⁷ will assess symptom severity among individuals with SMI. Potential changes in key cognitive domains associated with will be assessed with the MATRICS Consensus Cognitive Battery (MCCB). The Columbia Suicide Severity Rating Scale (CSSRS) will assess suicide ideation. Changes in mood symptomatology including also anhedonia and mania will be assessed with the Beck Depression Inventory (BDI), Snaith-Hamilton Pleasure Scale (SHAPS), and the Altman Self-Rating Mania Scale (ASRM) respectively. Changes in PTSD symptoms will be assessed using the PTSD Checklist for DSM 5.

Safety and Health-Related Measures. Adverse events (AEs) and severe AEs, along with concomitant medications, will be assessed at weekly study visits. Heart Rate (HR) and blood pressure (BP) will also be assessed using standard hospital-grade equipment.

Table 1. Outline of Study Procedures and Assessments.

Procedure and Assessments	Study Visits	Week 0	Week 1	Week 2	Week 3	Week 4	Week 5
Baseline Screening		X					
Receive E-Cigarettes (36 mg/ml) and NRT Patch (21 mg)				X	X	X	X
Smoking Related Assessments							

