Breath CO, QSU, MNWQ, , TLFB, CCQ, CQ, HONC		X	X	X	X	X	X
Urinary Cotinine		X					X
FTND, Stages of Change		X					X
E-Cigarette Questionnaires				X	X	X	X
AEs, Concomitant Meds, HR, BP		X	X	X	X	X	X
BPRS, CSSRS, BDI, SHAPS, ASRM, PTSD		X	X	X	X	X	X
MCCB		X					X

DATA ANALYSIS PLAN

Preliminary data analyses will inspect baseline, group differences as well as correlations between baseline variables and specified outcomes. Baseline or demographic variables demonstrating a correlation with both predictors and outcomes, meet criteria for being potential confounders,^{i,ii} and will result in two sets of analyses: one in which the relevant variable is included as a covariate and one in which it is not. This will determine the degree to which any group differences might confound conclusions regarding treatment. Statistical analyses will use R v. 3.3.0ⁱⁱⁱ and SAS v.9.3.^{iv}

Analyses will primarily use generalized linear modeling. Continuous, count, dichotomous and time-to-event data will utilize linear, Poisson, logistic, and proportional hazards regression respectively (Proc GENMOD and PROC PHREG; SAS v. 9.3, function glm(); R v. 3.3.0). Longitudinal analyses will employ generalized linear mixed models (Proc MIXED, Proc GLIMMIX and Proc MCMC; SAS 9.3). Evaluation of distributional assumptions will use residual plots and, where possible, formal statistical tests. Depending upon statistical technique, transformations, robust estimators, stratification and/or scaling coefficients will address violations of assumptions. Analyses of cross-sectional data with missing values will utilize multiple imputation (Proc MI; SAS v.9.3)^v. Multiple imputation and maximum likelihood are robust to data missing at random. Sensitivity analyses will permit evaluation of the robustness of findings to missing data assumptions.

Specific Aim 1: Assess feasibility, acceptability, and safety of providing e-cigarettes to adults with SMI to reduce tobacco smoking.

Hypothesis 1.a: We predict that a high proportion of participants will consent to participant (80%) and complete the study (70%) completion rate. Descriptive statistics will evaluate consent and completion rates.

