Hypothesis 1.b: We predict that end of study participant satisfaction ratings will indicate high acceptability of e-cigarettes and nicotine patch and likelihood of future use. Generalized linear models will evaluate the relationships between participant satisfaction, acceptability of e-cigarettes and nicotine patch, and likelihood of future use.

Hypothesis 1.c: We predict e-cigarettes will be safe as measured by frequency of adverse events (AEs) and side-effects, and not associated with increases in negative symptoms (BPRS) or decreases in cognitive performance (MATRICS). Generalized linear modeling will evaluate relationships between adverse events/side-effects, negative symptoms, and cognitive performance.

Specific Aim 2: To compare reductions in tobacco smoking between NRT vs NRT + e-cigarettes (36 mg/ml).

Hypothesis 2: *Significantly greater reductions in smoking (tobacco cigarettes/day, breath CO) will be observed in the NRT + e-cigarette vs. the NRT condition. Generalized linear modeling will evaluate group differences in smoking reduction between NRT and NRT + e-cigarettes over time as measured by breath CO (using a Gaussian distribution) and tobacco-cigarettes/day (using a Poisson distribution).*

Power/Sample Size Considerations. For the current proposal, power will focus on Aim 2. Effect size is derived using G*Power 3.1.9.2. Assuming alpha = 0.05 and a correlation among repeated measures of 0.5, a sample size of n = 20 (n = 10 NRT and 10 NRT + e-cigarette) provides 80% power to detect a Cohen's f = 0.51 for group differences between NRT and NRT + e-cigarette. The Frequentist findings will be augmented with a Bayesian approach to characterize the probability that effect sizes of varying magnitude exist.

JUSTIFICATION

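### The stated 80% power is not shown for Aim 2: f = 0.51 best matches a group average over five or six visits, and the covariate rule leaves the stronger baseline-adjusted analysis to chance

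*Combined protocol and SAP*

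**What the plan says.** Under Power/Sample Size Considerations, power is said to focus on Aim 2. With alpha 0.05 and a repeated-measures correlation of 0.5, "a sample size of n = 20 (n = 10 NRT and 10 NRT + e-cigarette) provides 80% power to detect" f = 0.51, obtained from G*Power. The paragraph gives no test, outcome, number of measurements or allowance for dropout. It adds that a Bayesian analysis will supplement the frequentist one.

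The Hypothesis 2 analysis concerns "group differences in smoking reduction between NRT and NRT + e-cigarettes over time", with breath CO as Gaussian and cigarettes/day as Poisson. The Data Analysis Plan adds: "Longitudinal analyses will employ generalized linear mixed models".

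The same section has a covariate rule: "Baseline or demographic variables demonstrating a correlation with both predictors and outcomes" count as potential confounders. Each leads to two analyses, one with the variable and one without.

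On timing, Study Design and Overview says: "Following a one-week baseline lead-in period, participants will be randomized". The Nicotine Replacement Therapy paragraph says: "Participants will receive nicotine patch (21 mg) starting study Week 1". In Table 1, the row that begins "Receive E-Cigarettes (36 mg/ml) and NRT Patch (21 mg" is first marked at Week 2, while breath CO and the smoking timeline are marked at all six visits, Weeks 0 to 5.

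Hypothesis 1.a predicts completion of at least 70%, that is 14 of 20.

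**The concern.** This is the only frequentist power statement for Hypothesis 2. A reader will take it to mean that a 1.02 SD difference on treatment (d = 2f) is detected with 80% probability in the planned analysis. That follows only if the test behind the number is the planned test. If the number came from a group average over every visit, pre-treatment visits, where no treatment effect can exist, would dilute the contrast.

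The plan also does not fix whether baseline smoking enters the Aim 2 model, and power depends heavily on that. The results are meant to support a later grant application, so a detectable effect attached to the wrong contrast could carry over into that design.

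**Working it through.** **Inputs.** From the power paragraph: N = 20 (n = 10 per arm), alpha 0.05, correlation ρ = 0.5, f = 0.51. From the schedule: six assessments. Assumed: equal correlation between all visit pairs, Gaussian outcome, no group difference before treatment, a constant difference of 1.02 SD on treatment. All powers use the noncentral F distribution.

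**1. Which test gives 0.51?** For the between-groups test over m measurements, λ = N f² m / [1 + (m − 1)ρ] with df 1 and 18. At m = 5, λ = 20 × 0.2601 × 5 / 3 = 8.67, power 79.5%.

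| m | power at f = 0.51 | f for 80% |
|---|---|---|
| 3 | 75.2% | 0.541 |
| 4 | 77.9% | 0.524 |
| 5 | 79.5% | 0.513 |
| 6 | 80.6% | 0.506 |
| 7 | 81.4% | 0.501 |

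Only m = 5 and m = 6 round to 0.51. The group-by-time test, λ = N f² m / (1 − ρ), gives 0.33 down to 0.24 for m = 2 to 6. One G*Power interaction option gives 0.512 at m = 3, but its formula does not use the correlation that the plan says it assumed.

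**2. How many visits are on treatment?** If the Week 1 assessment closes the lead-in, four visits remain (Weeks 2 to 5). An average over five or six visits then includes one or two pre-treatment visits, and f shrinks by 4/m:

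- m = 5: f = 0.51 × 4/5 = 0.408, λ = 20 × 0.1665 × 5 / 3 = 5.55, power 61%.
- m = 6: f = 0.51 × 4/6 = 0.340, λ = 20 × 0.1156 × 6 / 3.5 = 3.96, power 47%.

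**3. Contrasts closer to Aim 2.** With four post-dispensing visits, λ = 1.02² / (0.2 v), where v is the contrast variance in units of SD².

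| contrast | v | power |
|---|---|---|
| post mean, unadjusted | (1 + 3 × 0.5)/4 = 0.625 | 78% |
| change from one baseline | 0.625 + 1 − 1 = 0.625 | 78% |
| change from mean of two baselines | 0.625 + 0.75 − 1 = 0.375 | 94% |
| adjusted, one baseline | 0.625 − 0.25 = 0.375 | 93% |
| adjusted, two baselines | 0.625 − 0.25/0.75 = 0.292 | 97% |

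The adjusted rows use 17 df and allow for chance baseline imbalance; without that allowance they are 93.9% and 97.8%. The overall group-by-visit test has 59% (one pre-treatment visit) or 81% (two). If only three visits follow dispensing, the unadjusted post mean has 75% and the adjusted contrasts 90-95%.

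**4. Sensitivity to the pre-post correlation.** At 0.3 (other correlations 0.5), v for the adjusted contrasts is 0.625 − 0.09 = 0.535 or 0.625 − 0.09/0.75 = 0.505, giving 81% and 84%.

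**5. Detectable f, adjusted, four visits, two baselines.** With 20 participants, f = 0.37 at correlation 0.5. At pre-post correlation 0.3 that f has about 57% power, and 80% needs 0.37 × √(0.505/0.292) ≈ 0.49. With 14 completers, f is about 0.47 at correlation 0.5.

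**6. Dropout.** With 14 completers only, the between-groups test at f = 0.51 has 60-63% for m = 4 to 6, before any dilution.

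**7. The covariate rule.** For Aim 2 the predictor of interest is randomised group. A baseline variable can correlate with group only by chance: about 5% of the time if the criterion is p < 0.05. That threshold is an assumption, as the plan gives none. Even then, the adjusted model is only one of two analyses.

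**The case against.** The test is back-solved; the plan never names an average over all visits. A reader might infer that Aim 2 power is 61% or less, or that the calculation must have included pre-treatment visits. The documents support neither. Four on-treatment visits give 77.9%, close to the stated figure. If Week 1 counts as on treatment, six visits give 65.3%, and Weeks 1 to 5 alone give 79.5% with no dilution. The order of assessment and dispensing at Week 1 is not stated. For several sensible Aim 2 contrasts, 80% is about right or conservative. All of this stands, and it limits the point to what the plan has shown.

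The 14-completer figure is a lower bound, because the planned mixed models keep partial data. With 30% dropout and partial data kept, the unadjusted four-visit contrast has about 70-77%. The adjusted one has 88-97% at correlation 0.5, if each dropout contributes at least one post-dispensing visit.

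The gain from adjustment depends on the pre-post correlation. Entry requires at least 10 cigarettes/day and CO of at least 10 ppm, and such truncation could lower it. A replacement sentence quoting f = 0.37 alone could therefore overstate power. This also stands, and is why the fix asks for a range.

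Finally, this is a pilot with a fixed n and a Bayesian supplement. That lowers the stakes, but it does not say which model the 80% belongs to.

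**Conclusion.** The point holds in limited form. The stated inputs are best matched by a between-groups average over five or six measurements without dropout. That is not the Aim 2 contrast, and on the likeliest reading of the schedule it includes pre-treatment visits. The 80% is therefore not shown for Aim 2. A shortfall is not established: depending on the model left open, power for a 1.02 SD on-treatment difference runs from 47% to 97% with no dropout and correlation 0.5.

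The firmer part is the covariate rule. It makes use of baseline smoking a chance event, although prespecified adjustment would raise four-visit power from 78% to 93-97% at correlation 0.5, or to 81-84% at pre-post correlation 0.3. These figures assume a Gaussian outcome and a constant on-treatment difference, and do not cover cigarettes/day as Poisson. Severity is minor to moderate, confidence moderate.

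**What to change.** 1. Prespecify pre-treatment smoking (the value, or mean of values, taken before dispensing) as a covariate in the Aim 2 models, in place of the correlation-triggered rule.
2. Restate the power sentence for the baseline-adjusted group difference over the post-dispensing visits. Name the test, the outcome, the number of visits and the SD that defines f. Give the detectable f over a range of pre-post correlations and with 30% dropout. For four visits, two baselines and 20 participants, for example: about 0.37 at correlation 0.5 and about 0.49 at pre-post correlation 0.3; with 14 completers, about 0.47 at correlation 0.5. Say that this does not cover cigarettes/day analysed as Poisson.
3. Reconcile the Week 1 start in the text with the first product mark at Week 2 in Table 1, and say whether Week 1 assessments precede dispensing. This review does not choose between the two starts.

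The cost is one degree of freedom, one reworded paragraph and a schedule clarification. No extra participants, visits or measurements are needed.
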